# 10.3.4. Lotion sampling

The amount of lotion applied to limbs will be quantified in a series of three applications analogous to the Spray Sampling above. However, dosimeters are not required, nor are the

extensive practice sessions. The amount applied is the weight difference in the dispensing tube before and after application.

The instructions are as follows:

"Put a new latex glove on each hand. You will apply lotion to one arm only. The technician will tell you to which arm to apply. You will begin with an amount that you suppose is about one half of what you will need to achieve thorough and uniform coverage. After spreading that around the lower part of your arm, you will apply more as needed to the area closer to your elbow. Begin by gently squeezing lotion from a tube with the cap open directly onto the horizontally-held surface of the opposite arm. Hand the tube to the technician. Using the tips of the index and middle fingers, spread the lotion as evenly as possible on all surfaces of the lower arm. Do not spread it onto the hand or beyond the marking on your wrist. If you have sufficient lotion left to spread it evenly and thoroughly toward the elbow, continue in the direction. Do note spread it beyond the elbow or past beyond the marking near the elbow. If you need more lotion to achieve thorough and even coverage, make sure you have wiped all repellent from your fingertips onto the skin and ask the technician to hand you the tube. Apply as much additional as you think you need, as before, but to complete the coverage. If you decide that you have applied more repellent that you would normally use to achieve thorough and even coverage, immediately have the technician wash and dry the treated arm so that none of the repellent you have applied is visible on close inspection, and begin again. Likewise, be careful to avoid dropping any lotion off of the arm, and if this happens, begin again as you would if you applied too much.

After you have completed an application successfully, the technician wash and dry the treated arm so that none of the repellent you have applied is visible on close inspection, and reweigh the tube. You will continue until you have completed three successful applications. Then you will repeat the entire procedure above, but with the lower leg."

# 10.3.5 Equipment Used to Assess the Dosimetry Variable:

Passive dosimeters are 1.5 cm wide strips of 3M Brand NexcareTM HoldfastTM self-adhesive roll gauze attached to the adhesive side of 1.5 cm wide strips of 3M Brand clear packaging tape. The tape will retard test materials from passing from the dosimeter to the subjects' skin. The tape strip length will match the circumference of a given region of a subject's arm. The gauze strip will be 1.5 cm longer than the tape, in order to permit a 1.5 cm overlap onto the self-adhesive gauze bracelet, thus securing the dosimeter in place.

On the non-adhesive side tape strip (the inner surface of the dosimetry bracelet) the following notations will be made before they are used.

- a) Subject number
- b) L (for left placement) or R (for right arm placement)
- c) Position letter: a (wrist), b (next proximal), c (next proximal), d (elbow)
- c) T (for treatment) or C (for control)
- d) Replicate number (1, 2 or 3)

There will be eight bracelets per replicate. Each arm and leg will be treated three times. Each subject will therefore have a total of forty-eight custom bracelets made and labeled in advance.

Bracelets will be weighed before and after treatment on a traceably calibrated Sartorius H51 balance (measurement increment 0.0001 g, 30 g capacity). Test material containers (pump spray and aerosol) will be weighed before and after dispensing on a traceably calibrated Sartorius GC 2502 (measurement increment 0.001 g, 500 g capacity).

# 10.3.6. Repellency and LIBes:

Repellency is assessed in the field. Preparatory training of the subjects to recognize and remove mosquitoes that lite with intent to bite contributes to subject safety. Subject safety is also enhanced by brief periods of exposure at intervals. as well as careful dosing and application.

Subjects will have approximately one hour of training and practicing observing foraging mosquitoes and catching them from their own arms in a laboratory cage, using an aspirator. A researcher will first demonstrate the procedure using his or her own arms, and will be present to instruct and guide each subject throughout the exercise. Subjects will be shown how to place both arms in a screen cage and to turn on the aspirator using the switch on the handle. One mosquito will be released in the cage. A small area (less than ½ of the forearm) will be uncovered, with no insect repellent applied. Subjects will be instructed to carefully watch the mosquito as it flies in the cage. The subject will be instructed to carefully observe the mosquito as it lands on the skin, and to watch to see if its needle-like mouths are placed against the skin. Once a mosquito lands on the skin, places it mouth against the skin and stops walking, subjects will immediately attempt to catch the mosquito in the plastic nozzle of the mosquito catcher. They may practice as many times as they wish with additional mosquitoes, and the researcher will be certain that the use of the mosquito catcher is correct. After several captures of single mosquitoes, a maximum of two mosquitoes will be placed in the cage. Two LIBing mosquitoes may be readily captured after little practice. Two represents the maximum number of mosquitoes that may LIBe on limb before the exposure stopping rule is reached (below), and so the exercise in the cage with two mosquitoes is highly appropriate.

The mosquitoes used for this training are *Aedes aegypti* reared in the laboratory and free from diseases. The source colony of *Aedes aegypti* was established from eggs collected in Northern Thailand in 2004. F1 adults were tested by Vero cell (African green monkey kidney, *Cercopithecus aethiops*) plaque assay for possible transovarial infection of viruses. Typically, 20 females from subsequent generations are tested routinely, and no infection has been detected in the 2 years since this colony was established. A sample of 20 such females will be so tested before being employed in this study. Individual mosquitoes will not be used for more than one subject.

At the field site, the subjects and researchers will gather in an area without biting mosquitoes. Subjects are instructed not leave this area until guided by a researcher.

The technicians and other researchers who will assist subjects during the test will be introduced or reintroduced to the subjects. Subjects are instructed to call on them whenever they have questions. Each subject is given and must wear a head net, mesh jacket and pants, latex or vinyl gloves in their size, and is given an aspirator to suck any mosquitoes that land on treated skin and attempt to bite (LIBes) once formal exposures begin. A researcher will remind subjects about how to identify LIBes and when and how to operate the aspirator. Subjects will be further instructed about protecting themselves from mosquito bites during the test, and reporting on a mosquito that lands on skin treated with repellent.

Before the repellent is applied, subjects will be guided to wash the lower arms and/or legs with mild, low fragrance soap, rinsing them with a spray of ethyl alcohol (mixed with an equal part of water), and then drying them with a clean towel. A technician will then apply insect repellents to their forearms or lower legs to give even, complete coverage of the skin. The amount of repellent to be applied to any limb will be calculated in advance for each subject. The dosing rate will be the product of the subject's limb surface area multiplied by the grand mean (mean of subject means) rate calculated in the dosimetry data analysis for that test material. Each subject will therefore be dosed at the same rate within a given repellent even if their individual application rates differed from the grand mean.

Treated subjects will be partnered into groups of two. A researcher will then guide subjects into the area of the field site in which mosquitoes are active, approximately 15 minutes after the test materials are applied. Each member of a partner pair will watch their own exposed limbs and those of their partner for mosquitoes that land for one minute. A technician will advise subjects when the one-minute period begins and ends. Subjects will immediately remove any LIBing mosquitoes from the skin with repellent with the aspirator. They may also use the plastic

nozzle of the aspirator or a finger to interrupt any mosquito even more quickly.

At the end of the one-minute exposure period, subjects move away from the area with mosquito activity. Partners will assist one another in covering the treated skin with the sleeve of the net garments. Each subject will report the number of mosquitoes that attempted to bite their own treated skin during that one-minute period when asked by a technician who will record it on a data sheet. For perspective, note that in a typical test of a reasonably effective repellent, dozens of '0' LIBe values will be recorded for each '1' or '2'. In other words, during most exposure periods subjects do not experience close contact with mosquitoes.

Stopping Rule: Subjects are instructed to immediately cover exposed skin with the protective mesh provided if more than one LIBe occurs in a one-minute exposure period. Similarly, if subject receive a LIBe and recall receiving another in either of the two previous exposure periods, they are to ask their data recording technician to verify that recollection from the data record. If verified, the subject is instructed to immediately cover the limb as above.

Ambient LIBe pressure will be measured by experienced, untreated personnel from continuous exposure of a single limb during 1-minute periods commencing once every 15 minutes, beginning at the onset of data collection. Such negative control subjects are attended by two assistants who use mechanical aspirators switched on throughout the period to remove all mosquitoes that LIBe before biting commences. If mosquitoes are too abundant to permit ready aspiration, the controls may protect the exposed limb as soon as a LIBe occurs.

#### **10.3.7** Forms for Retention of Source Data:

Dosimety data will be recorded on data form for each test material formulation. 'Lite with intent to bite' (LIBe) data will be recorded on a repellency data form. Data forms are appended.

### 10.4 Study Facility:

Dosimetry data collection will take place in the main building and on the terrace of Carroll-Loye Biological Research.

#### 11 DATA ANALYSIS:

### 11.1 Experimental Unit:

The individual subject will be the experimental unit.

### 11.2 Replicates per Treatment:

For dosimetry, there will be 12 treated subjects, each serving as their own untreated control, testing each of the three repellent formulations. For repellency testing, there will be 10 subjects treated with each test repellent and two serving as untreated controls for repellency testing at each of two sites.

# 11.3 Statistical Methodology:

Statistics will be computed with the software 'SAS JMP' Version 5.0.1.2 (SAS Institute, Cary, NC).

# 11.3.1 Dosimetry:

Dosage will be calculated per square centimeter of skin. The amount of test material delivered to each dosimeter in each trial will be calculated as:

weight after application – weight before application

The **total captured** by all treated dosimeters per trial will be calculated by adding the mass changes in all four dosimeters together, and then subtracting or adding, respectively, any total gain of loss of weight in the paired control dosimeters.

The **proportion covered** of the total limb surface area by the dosimeters is:

Surface area of a set of 4 dosimeters
Surface area of the limb

The estimated **dosage per trial** is: **Total captured** x 1/**proportion covered** 

The specific gravity of each test material will be measured and used to convert the dosage weight data to volumes for preparing individual subject doses volumetrically for dispensing from the tuberculin syringes.

Subject means and standard deviations will be calculated for all measures of dosimeter weight changes as well as application behaviors (distance from nozzle to skin, duration of application, number of sweeps/pumps). Lotion, pump spray and aerosol statistics will be calculated separately and then compared with nonparametric tests for two- and three- sample independent cases (Wilcoxon match-pairs signed-rank and Kruskal-Wallis tests, respectively).

We will statistically assess the strength of any individual subject differences in application behavior and dosing in interaction with the three test materials using Friedman two-way analysis of variance subject dose means for each test material. We will use subject dose means for each test material to calculate dosing grand means (± SD) for each test material. Those means, expressed as repellent weight per unit skin surface area, will be used to determine individual subject doses in the field repellency test.

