# **5.2** Rationale and Main Endpoint:

This study will test the efficacy of new formulations of IR3535, created by the developer of IR3535, which are intended to increase cosmetic quality for better user acceptance. US/EPA requires new repellent formulations to be registered, and some registrants must present efficacy data as part of the registration review. The rationale for this study is to provide that efficacy data, which has not been previously collected. Compared to the insect repellent 'DEET' (N,N-diethyl-m-toluamide), there are few data examining the efficacy of IR3535 in different formulations. In addition, IR3535 has not been widely studied in the United States at end-product concentrations as high as those to be tested here. Yet the excellent

safety profile of IR3535 indicates that it is suitable for testing at higher concentrations than have typically been studied.

Stability of the end-products will be tested in a different study.

The main endpoint of this study will be the conclusion of a mosquito repellent efficacy study conducted in the field of three IR3535-based topical repellent formulations, with the data set suitable for submission to US EPA for insect repellent registration purposes. The efficacy study will consist of two field trials, with 10 treated subjects in each trial testing each formulation, and two untreated subjects in each trial. Initial dosage determination ('dosimetry') will be conducted with a set of 12 subjects, some of whom may then go on to participate in efficacy testing. Dosimetry will be conducted at the letterhead address. When 12 subjects have completed dosimetry, those data will be used to determine dosing for all efficacy trials with the actives, including those against other arthropods (i.e., including the tick repellent efficacy test, which is described in Carroll-Loye Protocol EMD-003). Protocol EMD-003, and this protocol, EMD-004, are independent in all other ways, except that individual subjects are not proscribed from participating in both studies.

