To summarize, adding subjects beyond six increases the precision of the means estimate only slowly. However, the individual and public health importance of avoiding inaccuracy in this study, coupled with the fact that data collection is only 'replicated' once (in a different habitat at that), argues for a prudent approach. To reduce the risk of over-representing atypically attractive subjects, as well the weight of the value obtained from any one subject, we regard 10 (rather than six) treated subjects as a better sample size for the repellency portion of the study. For dosimetry, in contrast to repellency, less general information is available, and the risk profile is more benign. Consequently, a slightly larger sample is prudent. In meetings with EPA toxicology staff in 2005, 12 was regarded as an acceptably sample size for estimating mean dosage for each to the repellent formulations. Accordingly, we propose to employ a total of 12 subjects for dosimetry.

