Work first with the pump spray, second with the aerosol spray. Because they are similar, the application instructions below describe the procedures for each type of spray together in each paragraph.

Familiarize yourself with the spray mechanism. Any actuation (pushing down on the pump plunger) of the spray must take place out-of-doors. Work at a distance of no less than 6 feet (1.9 meters) from other subjects. Do not dispense the spray at or near

your face or anyone else's. Minimize inhalation of airborne spray while working.

Testing will take place out-of-doors during daylight hours at an air temperature (shade) above 14 °C (57 °F) and wind speed below 12 kph (7 mph), with no precipitation. The researcher or a technician will inform you when these conditions are not met and spraying of the repellents will cease until those conditions resume.

Dispense the spray on one forearm, using the opposite hand. By successively moving the spray nozzle closer to and farther from the arm, identify a distance between nozzle and skin that seems most appropriate for effective application to the skin. The technician will measure and record that distance to the nearest centimeter on the provided datasheet.

Have the technician wash and dry the treated arm so that none of the repellent you have applied is visible on close inspection.

Now, using the spray nozzle at or near the distance from the skin that you have just chosen to be effective for application, determine the minimum number of actuations (pumps of the pump spray) or longitudinal passes (aerosol) required to give full coverage of all surfaces of the forearm. For the pump spray, depress the plunger fully each time, and count them aloud beginning with "1, 2, 3 ...." etc. If you partially depress the plunger (rather than fully depress it) in order, e.g., to apply to a small skin area not covered be initial application, report that to the technician as a "half pump." Each partial depression should be so reported as it occurs. If on any given actuation material fails to be delivered, do not count that actuation. If a partial amount is delivered, consider it either 'whole', 'half' or 'none' and report it as such. For 'none', simply resume counting at the next actuation that delivers material to the skin.

Report the count to the technician who will record it on the data sheet. The technician will also assist you in keeping track of whole versus half pumps.

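### The three-product dosimetry comparison uses Kruskal-Wallis on matched data, and the planned Friedman test cannot assess subject-by-product interaction; pump-before-aerosol order is also confounded with product

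*Combined protocol and SAP*

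**What the plan says.** The dosimetry data are matched. Section 5.2 describes one set of 12 people, section 9.1.3 concludes "we propose to employ a total of 12 subjects for dosimetry", and section 11.2 states "For dosimetry, there will be 12 treated subjects, each serving as their own untreated control, testing each of the three repellent formulations". Section 9.1.3 also gives 12 per formulation, which agrees with a total of 12 only if everyone tests all three products.

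Section 11.3.1 computes statistics separately for lotion, pump and aerosol and then has them "compared with nonparametric tests for two- and three- sample independent cases (Wilcoxon match-pairs signed-rank and Kruskal-Wallis tests, respectively". It goes on to assess "any individual subject differences in application behavior and dosing in interaction with the three test materials" with a Friedman analysis of the subject dose means. The grand mean of those subject means, by product, sets the field dose (sections 6.1.4, 10.3.6 and 11.3.1).

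On order, section 10.3.2 tells subjects: "Work first with the pump spray, second with the aerosol spray". The script finishes all pump work on arms and legs before repeating everything with the aerosol. Section 10.3.4 gives lotion no place in the sequence. No randomised or counterbalanced order is described.

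**The concern.** Three features do not fit a design in which each subject uses every product.

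- **Three-product test.** Kruskal-Wallis is an independent-samples test. It treats 36 subject means as coming from 36 people and leaves subject-to-subject variation in the error. Section 11.3.1 itself expects subjects to differ.
- **Interaction.** The plan wants to know whether subjects differ in how they dose with each product. The method named is a within-block rank test with one value per cell.
- **Order.** For the two sprays, any practice or fatigue effect is inseparable from product.

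At stake are the power to see a real difference in amount applied, an answer to the interaction question the plan itself raises, and the clean reading of the pump and aerosol means.

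**Working it through.** The plan gives no alpha, power, correlation or effect size for dosimetry, so there is no figure to reproduce. From the documents: n = 12 subjects, k = 3 products, one mean per cell. Assumed: alpha 0.05, normal data with total SD 1, within-subject correlation ρ from 0 to 0.9, and product shifts 0, δ/2, δ. The shifts are in total-SD units.

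**1. Why Kruskal-Wallis is conservative.** With N = 36 and rank sums R_j over all 36 values,

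H = 12/(36·37) · ΣR_j²/12 − 3·37 = ΣR_j²/1332 − 111, referred to chi-square on 2 df.

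That reference distribution assumes independence, under which a difference of two product means has variance 2σ²/12. Matching makes it 2σ²(1 − ρ)/12. At ρ = 0.5 the true variance is half of what the test allows for, and at ρ = 0.7 it is 30%. H is therefore too small under the null, and the benefit of matching is lost under an effect.

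Monte Carlo results with 20,000 replicates per row, chi-square reference for both tests, and power at δ = 0.75:

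| ρ | KW size | Friedman size | KW power | Friedman power |
|---|---|---|---|---|
| 0 | 0.048 | 0.061 | 0.31 | 0.27 |
| 0.3 | 0.016 | 0.057 | 0.26 | 0.36 |
| 0.5 | 0.006 | 0.058 | 0.22 | 0.48 |
| 0.7 | 0.001 | 0.059 | 0.18 | 0.69 |
| 0.9 | 0.000 | 0.057 | 0.14 | 0.99 |

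At δ = 0.8 the powers (Kruskal-Wallis against Friedman) are 30% against 40% at ρ = 0.3, 26% against 53% at 0.5, and 23% against 75% at 0.7. At ρ = 0.5, moving δ from 0.5 to 1.0 takes Kruskal-Wallis from 7% to 47% and Friedman from 24% to 72%. Friedman's size is slightly above 5% because of the chi-square approximation, which accounts for a small part of the gap.

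**2. The two-product test.** Wilcoxon matched-pairs signed-rank had size 0.037 to 0.049 over the same range of ρ (2,000 replicates per setting). It is valid for this design.

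**3. What Friedman can see.** With products as treatments and subjects as blocks,

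Q = 12/(12·3·4) · ΣR_j² − 3·12·4 = ΣR_j²/12 − 144,

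where R_j sums within-subject ranks.

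- *Subject differences.* Adding any constant to all of one subject's values leaves the ranks unchanged. In a check, p was 0.558 before and after adding large subject effects.
- *Interaction.* Take a pure crossing pattern in which four subjects follow each of three cyclic orderings. Each R_j = 4(1 + 2 + 3) = 24, so Q = 3·576/12 − 144 = 0 and p = 1. With random interaction of SD 0, 1, 3 and 10 times the error SD, the rejection rate stayed at 0.056 to 0.060.
- *Degrees of freedom.* 36 cells give 35 df: 11 for subjects, 2 for products, and 11·2 = 22 left. Those 22 are interaction and error combined, with no separate error term. This holds whichever factor is called the treatment.
- *Transposed.* With subjects as treatments and products as blocks, the test does respond to subject differences (rejection 0.63 at ρ = 0.5, 0.93 at ρ = 0.7), but it still gives no interaction test.

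**4. Order.** With no product difference and an assumed pump-to-aerosol order shift of 0.25 SD, signed-rank rejects 11% of the time at ρ = 0.5 and 15% at ρ = 0.7. With 0.5 SD it rejects 31% and 50% (3,000 replicates each).

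**The case against.** The strongest reply is that nothing in the study turns on these tests. The field dose is the grand mean for each product, section 10.3.6 applies it even to subjects whose own rate differed, and the efficacy analysis in section 11.3.2 is descriptive. That stands and limits the importance of the point. It does not cover the order effect, which would enter the means themselves.

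Second, the plan already contains a Friedman test on the right data. In its usual orientation that is the three-product comparison wanted here. This also stands: much of the power loss comes from assigning the wrong test to the question. As written, though, Friedman is given to a different question, and Kruskal-Wallis is the comparison that would be reported.

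Third, subjects practise with each spray before its sampling, and the technician reviews their earlier results with them. That should reduce a practice effect but cannot separate it from product.

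A reader might also infer more than the documents support:

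- *That both comparison tests are independent-samples tests.* Only Kruskal-Wallis is. The signed-rank test is paired and merely mislabelled.
- *That false positives are inflated.* The error runs the other way.
- *That Friedman can never show subject differences.* Section 11.3.1 does not state the orientation, and the transposed form can. The limit that holds in every orientation concerns interaction.
- *That all three products are in a fixed order.* Only pump before aerosol is documented.
- *That the interaction test decides whether one rate represents users.* That depends mainly on between-subject spread within a product, which the plan reports as an SD.

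**Conclusion.** The point holds for two stated analyses and one design feature. Kruskal-Wallis does not fit 12 subjects who each use three products. For correlations of 0.3 to 0.7 and a 0.8 SD spread, its size falls to about 2% to 0.1%, and its power is 30% to 23% where Friedman has about 40% to 75%. These figures rest on assumed alpha, correlation, effect size and normality; with no correlation there is no loss. Separately, and without any such assumption, a Friedman test on one mean per subject per product cannot assess subject-by-product interaction. Pump and aerosol are confounded with order; the size of any order effect is unknown.

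The documents do not support a conclusion that the field dose is invalid. The consequence is limited to the dosimetry comparisons, apart from a possible order effect on the spray means. The change is worth making because it is cheap.

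**What to change.** - Use Friedman, with products as treatments and subjects as blocks and preferably an exact p-value, for the three-product comparison. Use signed-rank for pairs, with a stated multiplicity rule such as Holm. Delete Kruskal-Wallis and the word *independent*.
- Drop the claim that Friedman assesses interaction. Fit a mixed model to the individual replicate applications, for example on log dose per unit area, with product and limb fixed and subject and subject-by-product random. The replicates supply the missing error term.
- State that lotion is measured by tube weight (10.3.4) and sprays by bracelet capture (11.3.1), so a lotion-spray contrast also carries measurement method. Reconcile the lotion replicates: section 10.3.4 describes one arm and then the lower leg, while the lotion form lists left and right arms and no legs.
- Counterbalance all three products. There are 3! = 6 orders, so 12/6 = 2 subjects take each. Otherwise state the pump-aerosol order as a limitation and say where lotion falls.

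The cost is revised analysis wording, an order list and edits to the script read to subjects. No added subjects are needed, nor applications beyond those planned once the lotion schedule is settled. The order must be settled before dosimetry starts, because no later analysis can separate it from product.
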